4.7. Rationale for Selection of Dose and Dose Range

For the once daily schedule, an initial dose range of 50 to 900 mg of LY2835219 administered orally once daily for 28 days was selected based on nonclinical toxicology and PK/PD data. For dose escalation on this schedule, there were 9 planned dose levels: 50, 100, 150, 225, 300, 400, 525, 700, and 900 mg administered orally every 24 hours for 28 days.

Table JPBA.4.3 summarizes the predicted median steady-state AUC and 90% prediction interval for the initially planned dose levels to be tested in Study JPBA. Exposure levels (AUC_{0-24 hr}) on Day 1 and at steady state in rats and dogs are summarized in the IB. Based on a starting dose of 50 mg given once daily and the *exposures on Day 1* at the Not Severely Toxic Dose in rats and highest Minimally Toxic Dose in dogs, the median predicted exposure multiples were approximately 52 and 1.8, respectively. Based on the *steady-state exposures* observed at these doses in rats and dogs, the exposure multiples predicted for this starting dose of 50 mg were approximately 106 and 4.2, respectively.

Preclinical efficacy associated with administration of LY2835219 was evaluated by 2 endpoints: 1) CDK4/6 inhibition (measured by the extent of phosphorylated Rb, topoIIα and pH3 inhibition) in xenograft tumors implanted in mice; and 2) exposure levels associated with xenograft tumor growth delay in mice. These efficacy parameters were integrated into a nonclinical PK/PD model.

Modeling the level of CDK4/6 inhibition associated with tumor growth delay in mice suggested that a clinical dose of 150 to 300 mg, administered once daily, should produce exposure levels demonstrated to produce the minimum level of CDK4/6 inhibition associated with efficacy in preclinical studies. Based on the *steady-state exposures* at the Not Severely Toxic Dose in rats

and the highest Minimally Toxic Dose in dogs, the median exposure multiples predicted at steady state for this clinical dose range were approximately 18 to 33 and 0.7 to 1.3 respectively.

In addition, PK/PD modeling suggested that AUC levels associated with tumor growth delay in preclinical *in vivo* efficacy studies (approximately 3600 to 9500 ng·hr/mL) should be reached in patients within a dose range of 300 to 700 mg administered once daily ([Table JPBA.4.3](#)). Based on the *steady-state exposures* observed at the Not Severely Toxic Dose in rats and the highest Minimally Toxic Dose in dogs, the median exposure multiples predicted at steady state for this clinical dose range were approximately 8 to 18 and 0.3 to 0.7, respectively.

During the dose escalation phase, preliminary analysis of PK data from the initial 4 dose levels (50, 100, 150, and 225 mg every 24 hours) indicated less than dose-proportional increases in exposure. Based on these results, a twice daily schedule was introduced in Part A with LY2835219 administered orally at the following planned dose levels: 75, 100, 150, 200, 275, 350, and 450 mg every 12 hours for 28 days. Importantly, the first planned dose level (75 mg every 12 hours) corresponded to a daily dose of 150 mg, which was 1 dose level lower than that of the highest previously explored dose level (225 mg every 24 hours). For the twice daily schedule, the highest dose of LY2835219 evaluated was 275 mg every 12 hours. At this dose level, 2 of the 3 patients experienced DLT of Grade 3 fatigue. At the next lower dose level of 200 mg every 12 hours, 1 of the 7 patients also experienced DLT of Grade 3 fatigue. Therefore, the maximum tolerated dose (MTD) was established at 200 mg every 12 hours.

During the tumor-specific expansion phases, patients initially received LY2835219 at the MTD of 200 mg every 12 hours. A preliminary interim safety review with data from 56 patients indicated that 29 patients experienced diarrhea possibly related to study drug: 17 Grade 1 (30%), 9 Grade 2 (16%), 3 Grade 3 (5%), none Grade 4 (0%), and none Grade 5 (0%). Based on the frequency of Grade 1/2 diarrhea and the observation of clinical activity at doses below the MTD, the initial starting dose was changed to 150 mg every 12 hours with JPBA amendment (f) to gain additional PK data and clinical experience around safety/tolerability. Importantly, diarrhea experienced by patients is manageable with standard anti-diarrheal agents. Therefore, early treatment with anti-diarrheal agents (e.g., loperamide) is recommended and the initial starting dose will return to the MTD of 200 mg every 12 hours with JPBA amendment (g).

Table JPBA.4.3. Predicted Steady-State Plasma Exposure Levels of LY2835219 in Humans Based on Daily Dosage Level

| Daily dose (mg) | Predicted AUC _{0-24 hr, ss} in Humans (ng·hr/mL) | |
|-----------------|---|-------------------------|
| | Median | 90% Prediction Interval |
| 50 | 450 | (200 – 1,000) |
| 100 | 900 | (400 – 1,900) |
| 150 | 1,450 | (550 – 3,000) |
| 225 | 2,000 | (900 – 4,600) |
| 300 | 2,700 | (1,200 – 5,800) |
| 400 | 3,650 | (1,600 – 8,100) |
| 525 | 4,700 | (2,100 – 10,400) |
| 700 | 6,250 | (2,700 – 13,800) |
| 900 | 7,800 | (3,500 – 17,200) |

Abbreviation: AUC _{0-24 hr, ss} = area under the concentration versus time curve from time 0-24 hours at steady state.

5. Investigational Plan

5.1. Study Population

5.1.1. Inclusion Criteria

Patients may be included in the study if they meet all of the following criteria:

[1] For all Parts: The patient must be, in the judgment of the investigator, an appropriate candidate for experimental therapy, either after available standard therapies have ceased to provide clinical benefit (Parts A, B, C, D, E, and F) or in combination with fulvestrant (Part G only).

For Dose Escalation (Part A): The patient must have histological or cytological evidence of cancer, either a solid tumor or a lymphoma, which is advanced and/or metastatic.

For Dose Confirmation (Parts B, C, D, E, F, and G): The patient must have histological or cytological evidence of one of the following cancers:

- Part B: Non-small cell lung cancer of any subtype that is advanced and/or metastatic.
- Part C: Glioblastoma multiforme (GBM) that has progressed or recurred after radiotherapy and/or chemotherapy.
- Part D: Breast cancer that is advanced and/or metastatic.
- Part E: Melanoma that is advanced and/or metastatic.
- Part F: Colorectal cancer that is advanced and/or metastatic.
- Part G: Breast cancer that is not only advanced and/or metastatic but also hormone receptor positive (HR+). The patient must be a postmenopausal woman with disease progression following anti-estrogen therapy and may be currently receiving fulvestrant at the time of study entry.

[2] Have the presence of measurable or non-measurable disease as defined by the Response Evaluation Criteria in Solid Tumors (RECIST 1.1, Eisenhauer et al. 2009) or the Revised Response Criteria for Malignant Lymphoma (Cheson et al. 2007),

For Parts A and G: Have measurable or nonmeasurable disease.

For Parts B, C, D, E, and F: Have measurable disease.

[3] Are ≥ 18 years of age.

[4] Have given written informed consent prior to any study-specific procedures

- [5] Have adequate organ function including:
 - Hematologic: Absolute neutrophil count (ANC) $\geq 1.5 \times 10^9/L$ platelets $\geq 100 \times 10^9/L$, and hemoglobin $\geq 8 \text{ g/dL}$. Patients may receive erythrocyte transfusions to achieve this hemoglobin level at the discretion of the investigator; however, initial study drug treatment must not begin earlier than the day after the erythrocyte transfusion.
 - Hepatic: Bilirubin ≤ 1.5 times upper limits of normal (ULN) and alanine aminotransferase (ALT) ≤ 3.0 times ULN.
 - Renal: Serum creatinine \leq ULN.
- [6] Have a performance status ≤ 1 for Dose Escalation (Part A) and ≤ 2 for Dose Confirmation (Parts B, C, D, E, F, and G) on the Eastern Cooperative Oncology Group (ECOG) scale (refer to [Attachment 6](#)).
- [7] Have discontinued all previous therapies for cancer (including chemotherapy, radiotherapy, immunotherapy, and investigational therapy) with the exception of fulvestrant (for Part G only) for at least 21 days for myelosuppressive agents or 14 days for nonmyelosuppressive agents prior to receiving study drug, and recovered from the acute effects of therapy (treatment related toxicity resolved to baseline) except for residual alopecia.
- [8] Are reliable and willing to make themselves available for the duration of the study and are willing to follow study procedures.
- [9] Males and females with reproductive potential must agree to use medically approved contraceptive precautions during the trial and for 3 months following the last dose of study drug.
- [10] Females with child bearing potential must have a negative serum pregnancy test within 3 days of the first dose of study drug.
- [11] Have an estimated life expectancy of ≥ 12 weeks.
- [12] Are able to swallow capsules.

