6.2.1. Dosing Schedule

For the once daily schedule, patients will continue to receive LY2835219 orally every 24 hours (± 3 hours) for Days 1 through 28 of a 28-day cycle. For the twice daily schedule, patients will receive LY2835219 orally every 12 hours (± 3 hours) for Days 1 through 28 of a 28-day cycle. For both schedules, there are modifications during Cycle 1 to enable PK sampling following a single dose and repeated doses.

During Cycle 1 on the twice daily schedule, the initial dose of study drug will be taken on Day -3 to enable PK sampling over 72 hours following a single dose; the remaining 55 doses will be taken every 12 hours on Days 1 to 28, with PK sampling on Day 1 and Day 15 and over 24 hours following the single dose taken on Day 28. For Cycle 1, patients should be specifically instructed not to take a second dose of study drug on Day 28; if such a dose is inadvertently taken on Day 28, it constitutes a protocol violation. Patients should not consume food beginning 1 hour before and ending 1 hour after taking study drug.

During Cycle 2 and beyond on the twice daily schedule, study drug is taken orally every 12 hours on Days 1 through 28 of a 28-day cycle.

During all cycles, study drug should be taken at approximately the same time(s) each day. If a patient misses or vomits a dose, that dose should be omitted. Patients must record the time and amount of each dose taken (or alternatively, the time and amount of the dose missed or vomited) in a daily diary.

For Part G, patients should receive fulvestrant according to the study schedule. For patients already receiving fulvestrant at time of study entry, the fulvestrant dose on Cycle 1 Day 1 should correspond approximately to the expected date for its monthly administration and fulvestrant should not be administered on Cycle 1 Day 15.

For Part G, fulvestrant 500 mg should be administered intramuscularly into the buttocks slowly (1 to 2 minutes per injection) as two 250-mg injections, one in each buttock; however, for patients with moderate hepatic impairment (defined as Child-Pugh Class B), fulvestrant 250 mg should be administered intramuscularly into the buttock slowly (1 to 2 minutes) as one 250-mg injection.

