- g Imaging studies are performed locally. Radiological tumor assessment is performed at baseline (Day -28 to Day-4), then between Day 21 and Day 28 (inclusive) of every other cycle beginning with Cycle 2; if necessary, radiological tumor assessment between Day 21 and Day 28 may be extended to Day 29 or Day 30 if the Day 28 procedures occur on Day 29 or Day 30, respectively (refer to footnote p for additional information). For patients with glioblastoma multiforme who are receiving corticosteroids (for example, dexamethasone), the baseline imaging study should be performed on a stable dose of corticosteroids. For patients with glioblastoma multiforme or brain metastases, radiological tumor assessment should also include MRI scan (preferred) or CT scan of the brain.
- h If a patient is discontinued from the study, repeat radiology may be omitted if progressive disease can be documented quantitatively with clinical measurements.
- i Request archived paraffin-embedded tumor tissue (to be used for assessment of tumor Rb and p-Rb status), but only after study eligibility is confirmed.
- j Only for patients in Parts B, C, D, E, F, and G. Pre-treatment biopsy should be obtained (whenever clinically feasible) between Day -14 and Day -4, but only after study eligibility is confirmed. Posttreatment biopsy should be obtained (whenever clinically feasible) between Day 8 and Day 22. Greater flexibility has been provided for the post-treatment tumor biopsy (15 ± 7) compared to other Day 15 assessments (15 ± 2) to enable radiographic guidance and access to appropriate medical specialists.
- k For central versus local labs, refer to [Attachment 2](#).

- o Follow-up starts just after the last dose of study drug and ends when final safety assessments are completed (30 ± 7 days after last dose of study drug).
- p If Day 28 procedures occur on Day 29 or 30, then these procedures are included in the current cycle and initiation of the next cycle is delayed until the following day.
- q For patients already receiving fulvestrant at time of study entry, fulvestrant dose on Cycle 1 Day 1 should correspond approximately to the date of its expected monthly administration.
- r For patients already receiving fulvestrant at time of study entry, fulvestrant should not be administered on Cycle 1 Day 15.

Continued Access Assessments

| Cycle/Visit | Cycles 501-5XX | | Continued Access Follow-up (901) | Comments |
|---|----------------|-------|----------------------------------|---|

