## 6.2. Populations for Analysis

Safety analyses will be conducted on all patients who have received at least one dose of LY2835219.

Pharmacokinetic analyses will be conducted on patients who have received at least one dose of the LY2835219 and have sufficient samples collected to allow the estimation of LY2835219 PK parameters.

Pharmacodynamic analyses will be conducted on patients who have undergone PD assessments.

Pharmacokinetic/Pharmacodynamic analyses will be conducted on the population of the PK analyses.

Efficacy analyses will be conducted on patients who have received at least one dose of LY2835219.

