**Table JPBA 6.1. Data Handling Conventions**

Term	Definition or Rule
Entered	Patients entered into the trial as those who sign the informed consent document directly or through their legally acceptable representatives.
Enrolled	Patients who are enrolled in the trial are those who have been assigned to a treatment.
On therapy	Patients who have received at least one dose of LY2835219.
Phase	This study has 2 phases: Dose Escalation Phase (Part A) and Dose Confirmation Phase (Part B, C, D, E F, and G).
Study day	
 
• There is no study day 0. Day -1 is the day before the day 1 of cycle 1 of each phase.
 
• Day -3 of cycle 1 of Dose Escalation Phase is the first dose of LY2835219.
 

Cycle day	
 
• There is no cycle day 0. Cycle day -1 is the day before the cycle day 1 of cycle 1 of each phase.
 
• Day -3 of cycle 1 is the first dose of LY2835219 in each phase. Day 1 of cycle 2 and beyond is the first dose of LY2835219 within cycle for each phase.
 

Treatment Day	Treatment Day relative to first day of the study (Cycle 1 Day -3).
Baseline	
For change from baseline analyses, baseline value is defined as the last reported measure on or before the first dose date (prior to the dose administration), unless otherwise specified.
 
For change from baseline within a cycle, baseline value is defined as the measure prior to the first dose of that cycle, unless otherwise specified.

The following are the General Reporting Requirements for the non-PK analyses (Table JPBA.6.2).

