### **6.3.9. Efficacy**

Efficacy assessments will be derived for patients during Dose Confirmation Phase (Parts B, C, D, E, F, and G).

Eastern Cooperative Oncology Group performance status (PS) will be listed and summarized for patients on therapy by cohort and cycle.

Reported lesion data (target or non-target) and investigator evaluation will be listed for patients on therapy.

Tumor markers will be listed for patients on therapy.

The best overall response, duration of overall response, duration of overall CR and duration of SD will be listed for patients on therapy. If appropriate, the efficacy endpoints, including Overall Response Rate, Disease Control Rate, Duration of Overall Response, Duration of

Overall CR, Duration of Stable Disease, PFS, and OS, will be summarized for Parts B, C, D, E F, and G.

The Overall Response Rate is defined as the proportion of patients who exhibits a confirmed CR or PR relative to baseline as defined by RECIST Version 1.1 (Eisenhauer et al. 2009). A responder is defined as any patient who exhibits a confirmed CR or PR relative to baseline assessment.

Disease Control Rate is defined as the proportion of patients in the analysis population who exhibit a SD or confirmed CR or PR relative to baseline during the study. Response is defined by RECIST Version 1.1 (Eisenhauer et al. 2009).

Overall Response Rate and Disease Control Rate with their respective 95% CI will be estimated using the Clopper-Pearson method. For time to event endpoints, including Duration of Overall Response, Duration of Overall CR, Duration of Stable Disease, PFS, and OS, the survival curve will be estimated by the Kaplan-Meier method (Kaplan and Meier 1958). Quartiles and rates at time points of every 3 months, together with the 95% CIs, will be provided.

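### The baseline imaging window opens up to 11 days before prior anticancer therapy must have ended, so tumor change from treatment given after the scan can be counted as response to LY2835219.

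*Protocol*

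**What the plan says.** **Washout.** Criterion [7] in Protocol Section 5.1.1 applies to patients who "Have discontinued all previous therapies for cancer (including chemotherapy, radiotherapy, immunotherapy, and investigational therapy) with the exception of fulvestrant (for Part G only"), and sets the interval as "for at least 21 days for myelosuppressive agents or 14 days for nonmyelosuppressive agents prior to receiving study drug". The clock runs back from study drug. The criterion also asks for recovery from acute treatment toxicity, but says nothing about imaging.

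**First dose.** Protocol Section 6.2.1 states for the twice daily schedule, which the expansion cohorts use, that "the initial dose of study drug will be taken on Day -3 to enable PK sampling over 72 hours following a single dose". SAP Table JPBA 6.1 agrees: "Day -3 of cycle 1 is the first dose of LY2835219 in each phase".

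**Baseline imaging.** Attachment 1, footnote g: "Radiological tumor assessment is performed at baseline (Day -28 to Day-4"). Footnote b gives the same window for radiological assessment including chest X-ray.

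**Analysis.** SAP Table JPBA 6.1 says that for change analyses the "baseline value is defined as the last reported measure on or before the first dose date (prior to the dose administration), unless otherwise specified". SAP Section 6.3.9: "A responder is defined as any patient who exhibits a confirmed CR or PR relative to baseline assessment". SAP Section 6.2: "Efficacy analyses will be conducted on patients who have received at least one dose of LY2835219". None of these refers to the date on which prior therapy ended.

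**The concern.** The washout and the imaging window are anchored separately, and they overlap. A patient may have the baseline scan, then receive further anticancer treatment, then observe the full washout and start LY2835219 without breaking any rule. The scan then describes the tumor before the other treatment had finished. Any later shrinkage from that treatment is measured against this scan.

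Documenting antitumor activity is a secondary objective. It rests on single-arm cohorts, where no control group would show shrinkage arising from something else. Confirmation at least 4 weeks later guards against a one-off measurement error. It would not remove shrinkage that lasts.

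The protocol accepts the principle elsewhere. Section 9.2 says that earlier fulvestrant confounds response and progression in Part G. Footnote g asks for a stable corticosteroid dose at baseline imaging in glioblastoma. There is no matching rule for anticancer treatment given after the baseline scan.

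**Working it through.** The plan states no figure for this gap, so there is none to reproduce. The check is calendar arithmetic on the plan's own days. All the days are negative, so the absence of a Day 0 has no effect.

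**Inputs**
- First dose: Day -3 (Protocol 6.2.1; SAP Table JPBA 6.1).
- Washout: 14 days for nonmyelosuppressive and 21 days for myelosuppressive agents (Protocol 5.1.1 [7]).
- Earliest baseline scan: Day -28 (Attachment 1, footnotes b and g).
- Expansion cohort size: at least 15 and up to 45-60 (Protocol 6.2.3).

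**Formulas**
- Last permitted prior-therapy day = first dose day − washout.
- Maximum gap = last permitted prior-therapy day − earliest scan day.

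| Class | Last permitted day | Maximum gap | Gap if full treatment-free days are required |
|---|---|---|---|
| Nonmyelosuppressive | -3 − 14 = Day -17 | -17 − (-28) = 11 days | -18 − (-28) = 10 days |
| Myelosuppressive | -3 − 21 = Day -24 | -24 − (-28) = 4 days | -25 − (-28) = 3 days |

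Radiotherapy is named in criterion [7], but the two intervals are worded for agents and it is placed in neither class. Its maximum gap is 11 days if it is handled under the 14-day interval and 4 days if under the 21-day interval.

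**Effect on ORR.** With the denominator fixed at all dosed patients, one patient wrongly counted as a responder adds 1/n:
- n = 15: 1/15 = 6.7 percentage points
- n = 45: 1/45 = 2.2 percentage points
- n = 60: 1/60 = 1.7 percentage points

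**Does another rule close the gap?**
- The SAP baseline rule takes the last measure before dosing. A later scan would replace an early one, but none is required.
- The efficacy population is everyone dosed, so no one is removed because of scan timing.
- Exclusion [17] concerns stability of CNS disease in the 14 days before study drug. It does not order the scan after prior therapy.
- Palpable and visible lesions are measured, as the schedule reads, in the Day -14 to Day -4 column, after the last permitted prior dose. The gap therefore concerns imaged lesions only.

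**The case against.** The strongest reply is that the sequence is possible but not shown to occur. It needs an early scan, anticancer treatment after that scan, and a delayed effect large enough to be a confirmed response. Criterion [1] narrows it further: in Parts A to F, available standard therapies must no longer be helping the patient, so delayed shrinkage from failed systemic therapy is unlikely. In Part G the protocol already labels response results as descriptive only because of earlier fulvestrant. The analyses are descriptive throughout, and the SAP summarizes efficacy endpoints only if appropriate. Response follows RECIST 1.1, which is not among the documents, so any limit it puts on treated lesions cannot be checked here.

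Most of this stands and limits the point. It leaves the route through local radiotherapy to a measured lesion, which criterion [1] does not bar. Palliative radiotherapy is foreseen in this population, since Section 6.5 permits it even on study.

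Three stronger readings are tempting, and the documents do not support them:
- **A reader might infer that one such patient lifts a 15-patient cohort past an ORR threshold of 5%.** In Section 9.1.1, 5% is the planning value for marker-absent tumors in a comparison of marker groups. It is not a decision limit for a whole cohort, and any single responder among 15 exceeds it.
- **A reader might infer that progression-free survival is shortened for the same reason.** Growth between scan and first dose arises with any screening window. Here the scan may precede dosing by up to 25 days (-3 − (-28)), even in a patient whose therapy ended long before. Ordering the scan after prior therapy would not remove that.
- **A reader might infer that affected responses can be struck out lesion by lesion.** That needs a link between irradiated sites and target lesions, which the documents do not say is collected.

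**Conclusion.** The gap is real. A compliant baseline scan can come before the last prior treatment by up to 11 days for nonmyelosuppressive agents and 4 days for myelosuppressive agents. For radiotherapy the figure is 4 or 11 days, depending on a classification the protocol does not make. If the washout means full treatment-free days, the figures are 10 and 3.

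The consequence is that tumor change from treatment given after the scan can be counted as response to LY2835219. The documents do not show that it has been: the number of patients affected is unknown. Each one would add 6.7, 2.2 or 1.7 percentage points to ORR at 15, 45 or 60 patients. This assumes that the patient would not otherwise have responded and that no later scan replaced the early one.

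The point bears on a secondary, descriptive objective. The primary safety objective is unaffected. It merits correction because the scheduling rule itself permits the misclassification and the remedy is small.

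**What to change.** **Protocol.** In Attachment 1, footnotes b and g, add: the baseline radiological assessment must be performed after the last dose of any prior anticancer therapy, including radiotherapy, except fulvestrant in Part G. The exception is needed because criterion [7] exempts fulvestrant and Part G patients may enter while receiving it.

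**SAP.** For patients already enrolled, derive a flag for those whose baseline scan date precedes their last prior-therapy date, again excepting fulvestrant in Part G. Report the number flagged by cohort, and give ORR and DCR with and without them as a sensitivity summary. If accrual is complete, this is the useful part, because the count shows whether the problem arose.

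**Cost.** One sentence in the schedule and one derived flag. The SAP already plans listings of prior radiotherapies, systemic therapies and lesion measurements, so new collection should not be needed provided those records carry dates. A patient at the minimum washout keeps an imaging window of about Day -17 to Day -4, or Day -24 to Day -4 under the 21-day interval. An occasional screening scan will be done later or repeated, and ORR may be slightly lower.
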